12.1.1.5 Clarification of the difference in meaning between "severe" and "serious"

The terms "severe" and "serious" are not synonymous:

- **"serious"** is **based on patient/event outcome** or action criteria usually associated with events that pose a threat to a patient's life or functioning. "Seriousness" (not severity) serves as a guide for defining regulatory reporting obligations.
- **"severe"** is used to **describe the severity** e.g. intensity of a specific event, which could be rated ***mild, moderate or severe***. The event itself, however, may be of relatively minor medical significance (such as severe headache).

12.1.2 Guidelines for reporting Adverse Events

All AEs, whether or not considered by the investigator to be related to the study drug, must be **recorded in the patient's medical records and in the CRF**. For each adverse event, the reported term, onset and end dates, severity, consequences on study drug intake (action taken), relationship to study drug, outcome and information on seriousness of the event will be recorded.

The severity, the relationship to the study drug and the outcome of the adverse event will be assessed by the investigator.

- **The severity** (intensity) of each AE must be assessed according to the following classification:
 - **Mild**: does not interfere with routine activities,
 - **Moderate**: interferes with routine activities,
 - **Severe**: patient is unable to perform routine activities.
- **The relationship** of any adverse effect to the study drug must be assessed according to the following rating:
 - **Unrelated /unlikely**: clearly and incontrovertibly due only to extraneous causes and does not meet criteria listed under possibly or likely related.
 - **Possibly / probably related**: follows a reasonable temporal sequence from administration of the study intervention, follows a known or expected response pattern to the suspected intervention, but that could readily have been produced by a number of other factors.
 - **Related**: clearly related to the investigational agent or the studied procedure, i.e. an event that follows a reasonable temporal sequence from administration of the study intervention, follows a known or expected response pattern to the suspected intervention, which can be confirmed by an improvement upon stopping the Investigational Product and reappearance of the event after rechallenge and that could not be reasonably explained by the known characteristics of the subject's clinical state.
- **The outcome** of each AE must be assessed according to the following classification:
 - **Ongoing***: the AE has not resolved,
 - **Recovering**: improvement in the patient's condition has occurred, but the patient still has some residual effects,
 - **Recovered without sequelae**: the patient has fully recovered with no observable residual effects,
 - **Recovered with sequelae ****: the AE has resulted in a permanent impairment
 - **Death**: the patient died due to the AE,
 - **Unknown**: the outcome of the AE is not known because the patient did not return for follow-up (lost to follow-up),

* If an AE is still on-going at the last visit, the patient must be followed up until the outcome can be documented without using "on-going" in the assessment.

* * A description of sequelae must be provided in the e-CRF

In order to ensure the safety of the patients, the investigator should take appropriate measures to follow all AEs until clinical recovery is complete and laboratory results have returned to normal, or until progression has been stabilized, or until death. This may imply that observations will continue beyond the last planned visit per protocol, and that additional investigations may be requested by the monitoring team as it may be asked by the sponsor.

12.1.3 Guidelines for reporting Serious Adverse Events

All **Serious Adverse Events**, whether or not deemed drug-related or expected, **must be notified immediately or within 24 hours**) of becoming aware of the event to the global pharmacovigilance representatives of the sponsor. The investigator must inform the site monitor. The initial notification must be followed within **additional 24 hours by a written report, using the study specific SAE Report Form**, providing all available information and detailed narrative description. Any medically relevant follow-up information must be reported within the same timelines.

After the initial report, the SAE should be promptly described in a detailed written report including all data allowing the event to be documented and using only the anonymous copies (with only the subject identification code: treatment number and initials) from hospitalisation reports and additional performed examination(s). The investigator should also report all elements concerning the follow-up of the SAE.

When reporting a death, the investigator should supply any additional requested information such as autopsy reports (if available) and final medical reports.

The "**Serious Adverse Event**" form and the instructions on completion are provided in the investigator's study file. The "Instructions for Completing the SAE Form" give more detailed guidance on the reporting of SAEs, significant overdose cases, and AEs initially reported as non-serious which become serious.

The Global Pharmacovigilance Representative of the Sponsor will forward any SAE initial and/or follow-up notification/report to Pharnext to the attention of the Chief Medical Officer within one working day, and will also ensure compliance with all regulatory reporting requirements and notify the authorities, ethics committees and investigators as appropriate. All safety reporting responsibilities, timelines and procedures will be in detail described in study specific Safety Management Plan.

12.1.4 Follow-up of Adverse Events

Patients experiencing adverse events will be monitored with relevant clinical assessments and laboratory tests prescribed by the treating physician. The investigator will ensure that follow-up includes any supplemental investigations that might be necessary to investigate the nature and/or causality of the AE/SAE.

All adverse events (including SAEs) must be followed until satisfactory resolution or stabilization.

Any measure taken and follow-up result must be recorded in the patient's CRF, as well as in the patient's source document. Follow-up laboratory results should be filed with the patient's source documentation.

12.2 Vital signs

Vital signs including systolic and diastolic blood pressures (measured in supine position after 10 minutes rest) and heart rate will be measured at each visit. Body weight will be measured only at the screening. Measurements will be recorded in the e-CRF.

12.3 Physical examination

A complete physical examination will be performed at the screening visit (V0) and at each visit for the purpose of observing the patient's overall appearance, general health and behaviour. The examination includes cardiovascular, respiratory, abdominal, neurological, locomotive and dermatologic systems. Any significant abnormalities should be recorded in the eCRF.

12.4 Electrocardiogram (ECG)

An ECG will be performed at the screening visit (V0) and at the end of the single blind treatment (V6 or at early withdrawal visit) using the internationally recognised 12-lead ECG recording which includes date, time, initials of the technician/nurse, initials of the investigator or their deputy, at least 2 complexes for each lead and a single lead run. The corresponding source data will consist of the Cardiograph paper print-outs that should be kept in the file and a copy should be provided to Pharnext (sent to centralized reading center). Main ECG parameters including heart rate, sinus rhythm PR, QRS, QT and QTc interval will be analysed by a cardiologist in the central reading center.

12.5 Laboratory tests

A full laboratory test should be performed at screening visit (V0), at 6-month (V3), 12-month (V5) and 15-month (V6) visits, or at early withdrawal visit.

The following blood parameters should be evaluated:

- **hematology**: red blood cell count, hemoglobin, hematocrit, platelet count (absolute), white blood cell count and white blood cell count differential
- **biochemistry tests** (serum/plasma): Sodium (Na), Potassium (K), Chloride (Cl), Gamma-glutamyl-transpeptidase (γ GT), Alanine aminotransferase (ALAT), Aspartate aminotransferase (ASAT), Alkaline phosphatases, Urea, Creatinine, Total Bilirubin and Blood glucose.

Standard blood tests (including pregnancy test at screening and last treatment visit) will require **12 ml of blood at each sampling** (screening, 3 months, 6 months, 12 months and final follow-up visit (see Study Flow chart)).

Laboratory examinations will not be repeated at the inclusion visit if already performed at screening within 14 days.

Follow-up of laboratory test abnormalities:

The subject's best interests will always be the first priority, before those of the trial. Abnormalities of any laboratory tests considered to represent a significant danger to the subject will lead to immediate discontinuation of the drug and the study monitor and sponsor must be informed immediately.

In the event of abnormalities considered not to represent a danger, continuation of the drug can be allowed after a discussion with the study monitor. These subjects will be followed-up by an appropriate medical management until they return to normal or baseline values or if a clinical diagnosis of an undercurrent illness is confirmed. The results of all known laboratory tests required by the protocol will be held / recorded in the subject's e-CRF. All clinically important and abnormal laboratory tests which occur during the study will be repeated at appropriate intervals until they return to baseline or to a level deemed acceptable by the investigator and the study monitor.

12.6 Pregnancies

A **pregnancy test** will be performed at screening and at the end of treatment for all women of child

bearing potential. During all the study, these women should use highly effective method of birth control. Study participants who become pregnant during the study must be withdrawn.

Every newly diagnosed pregnancy of a study subject has to be reported via a '**Pregnancy Re-port Form**' which must be submitted within 24 hours of learning of its occurrence to the Global Pharmacovigilance Representative of the Sponsor. A newly diagnosed pregnancy in a patient that has received a trial medication is not considered a serious AE, unless meeting any criteria of seriousness or if it is suspected that the trial medication interacted with a contraceptive method and led to the pregnancy.

The pregnancy must be followed up to determine outcome, including spontaneous abortion or voluntary termination, details of birth, and the presence or absence of any birth defects, congenital abnormalities or maternal and new-born complications. Every infant has to be followed for 2 months after delivery.

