11.2.3 Visit 2 at 3 months

The visit at 3 months is essentially for drug dispensation, checking safety (AEs) and treatment

compliance. Eventually, if local regulations allow that the dispensing of medication can be organized by shipping, these intermediate visits at 3 months may be made by phone call.

The investigator has to interview the patient and to detect the occurrence of potential adverse events, or any change in the concomitant treatments.

The patients will be asked whether the investigational treatment was taken as prescribed. If not, any change in the treatment and the number of forgotten intakes will be recorded. In addition, the number of used and unused bottles will be counted and compared to the theoretical quantities that should be used according to the time from last visit. Any mismatch will be investigated and justified in collaboration with the patient if possible.

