11.2.4 Visit 3 at 6 months

The following assessments must be performed:

- physical and neurological examination including vital signs (SBP and DBP, heart rate),
- electrophysiology testing of sensory and motor responses of ulnar and radial nerves on the non-dominant side, including CMAP, SNAP, NCV, and DML parameters.
- clinical scores and functional tests will be assessed:
 - ONLS score
 - CMTNS score
 - 9-Hole Peg Test in non-dominant limb
 - Quantified muscular testing (hand grip and foot dorsiflexion on both sides)
 - 10 m Walking test
- quality of life measured by:
 - EuroQol 5-Dimensional Health-related Quality of Life scale (EQ-5D);
 - VAS on self-assessment of the individualized main impairment in daily activities defined at baseline with the patient;
- review of concomitant treatments
- review of Adverse Events
- blood sample for biomarkers
- blood samples for PK (one before dosing, and one 90 minutes after drug intake)
- blood sample for safety
- review of compliance to study drug and drug accountability: the patient will be asked whether the investigational treatment was taken as prescribed. If not, any change in the treatment and the number of forgotten intakes will be recorded. In addition, the number of used and unused bottles will be counted and compared to the theoretical quantities that should be used according to the time from last visit. Any mismatch will be investigated and justified in collaboration with the patient if possible.

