11.5 Follow-up for withdrawn patients

When a subject is prematurely withdrawn from the study, before *V6 at 15 months*, the investigator must perform a complete "end of study visit" (as soon as possible) after patient withdrawal.

The Investigator must make every effort to contact patients lost to follow-up. Attempts to contact such patients must be documented in the patient's records (e.g., times and dates of attempted telephone contact, receipt for sending a registered letter). Particularly, effort must be done to obtain data on patient's health status (death: yes/no) and to determine the reason why he/she failed to attend the visit. If death occurs, a death certificate will be collected by the investigator.

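### Low-priority, cheap safety improvement: no pregnancy test is scheduled during 440 to 460 days of dosing; testing the safety blood already drawn at V3 and V5 would cut the longest on-treatment interval to 200 days

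*Combined protocol and SAP*

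**What the plan says.** Two sections of the protocol set the pregnancy testing schedule, and they agree. Section 12.6 says the test "will be performed at screening and at the end of treatment for all women of child" bearing potential. Section 12.5 says: "Standard blood tests (including pregnancy test at screening and last treatment visit) will require" 12 ml at each sampling. The visit lists in sections 11.2.2 to 11.2.7 and the flow chart in section 3 do not mention a pregnancy test.

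Section 12.6 also states the consequence: "Study participants who become pregnant during the study must be withdrawn". Each new pregnancy must be reported within 24 hours of being known and followed to outcome, and each infant is followed for 2 months.

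Safety blood is drawn more often than the pregnancy test is done. Section 12.5 says: "A full laboratory test should be performed at screening visit (V0), at 6-month (V3), 12-month (V5) and 15-month (V6) visits", or at early withdrawal. The lists for V3 (11.2.4) and V5 (11.2.6) both include a "blood sample for safety". For patients who leave early, section 11.5 says "the investigator must perform a complete" end-of-study visit. Read with section 12.5, this implies a pregnancy test at that visit.

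**The concern.** The withdrawal rule can act only on a pregnancy that someone knows about. For a completer, the schedule has no test between screening and the end of dosing, so during treatment the rule depends on the participant or the investigator suspecting a pregnancy. A test at V6 comes when dosing in this study is ending, and withdrawal can then no longer prevent exposure.

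What is at stake is foetal exposure to study drug, and the timely reporting and follow-up that section 12.6 asks for. The efficacy analysis, the error rates and the sample size are not affected.

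**Working it through.** The documents state no interval between pregnancy tests, so there is no plan figure to reproduce beyond the visit windows.

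**Inputs**
- First dose at V1, Day 0 (section 11.2.2); dosing continues to the last visit (section 10.5).
- V0 on Day -30 to -1; V3 on Day 180 ± 10; V5 on Day 360 ± 10; V6 on Day 450 ± 10 (synopsis and section 11.1). A shifted visit does not move the next one, so an early V3 can be followed by a late V5.
- Contraceptive failure below 1% per year (exclusion criterion 10, section 9.2).
- Allocation 1:1:1, so one third receive placebo (synopsis).
- Planned last patient out: Q1 2018, except Germany in Q3 2018 (synopsis). Version 1.4 is dated 5 December 2017.

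**Interval under the plan.** Dosing without a scheduled test: 450 ± 10 = 440 to 460 days.

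**Interval with tests at V3 and V5**
- V1 to V3: 170 to 190 days.
- V3 to V5: 350 - 190 = 160 to 370 - 170 = 200 days.
- V5 to V6: 440 - 370 = 70 to 460 - 350 = 110 days.
- Longest on treatment: 200 days.
- Test to test from screening, V0 to V3: at most 190 + 30 = 220 days.

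**Expected pregnancies at the 1% ceiling, per 100 women of childbearing potential**
- 100 × 0.01 × 440/365.25 = 1.20; for 450 days 1.23; for 460 days 1.26.

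**How many could gain.** The unrecognised share is not in the documents; 5% to 25% is assumed. Conception is taken as equally likely on any day from 0 to 450. A conception after V5 meets the V6 test under either schedule and gains nothing, so only 360/450 = 80% count.
- 1.23 × 0.80 × 0.05 = 0.05; 1.23 × 0.80 × 0.25 = 0.25 per 100 women.
- On active drug under 1:1:1 (× 2/3): 0.03 to 0.16 per 100 randomised women.
- At version 1.4, with dose 2 leaving and dose 1 and placebo continuing, about half are on placebo (× 1/2): 0.02 to 0.12 per 100 continuing women.

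**Reach at version 1.4.** V5 falls 70 to 110 days before V6. V3 falls 440 - 190 = 250 to 460 - 170 = 290 days before V6. Taking the last day of each planned quarter as last patient out:

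| | Last V3 | Last V5 |
|---|---|---|
| Outside Germany (31 March 2018) | 14 June to 24 July 2017 | 11 December 2017 to 20 January 2018 |
| Germany (30 September 2018) | 14 December 2017 to 23 January 2018 | 12 June to 22 July 2018 |

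Outside Germany, V3 is past and few V5 visits remain. In Germany some V3 and many V5 visits may still lie ahead, although the interruption there may have shifted these dates.

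Section 12.5 also mentions a 3-month blood sampling that the flow chart lacks. This does not change the result, because that section ties the pregnancy test to screening and the last treatment visit only.

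**The case against.** The strongest reply is that the risk is already managed. Highly effective contraception and willingness to be tested are entry conditions (exclusion criterion 10), so a test on suspicion is foreseen. Patients are told to phone if an adverse event occurs (11.2.2). At month 3, "The investigator has to interview the patient and to detect the occurrence of potential adverse events", and month 9 repeats this. V3 and V5 include adverse event review, and section 12.3 says: "A complete physical examination will be performed at the screening visit (V0) and at each visit", covering the abdomen among other systems. All of this stands, and it keeps the gain small. But contraception lowers incidence without detecting failures, and the other measures depend on someone noticing. None is a scheduled test.

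A second reply is that no need for denser testing is shown. Section 6.5 names no reproductive hazard, refers to the Investigator Brochure, and puts component doses 5 to 35 times below approved use. That also stands. Two extra tests are a reasonable choice, not a frequency derived from toxicity data.

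A third reply concerns cost. Section 16.2 has the information letter state the type and number of scheduled examinations, and section 15.4 requires sponsor and EC/IRB approval before changed patient documents are used. Section 15.5 lets a risk-reducing amendment start early but does not say the same for those documents. With at least 20 centres (8.2) and few visits left outside Germany, this is a fair limit on what the change can achieve.

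A reader might also infer that an unrecognised pregnancy would remain on study drug until V6, perhaps for more than a year. The documents do not support that. Assuming about 266 days from conception to term, any conception before about Day 184 (450 - 266), or 184/450 = 41% of conceptions spread evenly over dosing, would end before V6. The contacts listed above also make earlier recognition likely. The 440 to 460 days describe the test schedule, not the length of exposure.

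**Conclusion.** The gap is real and visible in the text: a completer has no scheduled pregnancy test during 440 to 460 days of dosing, while section 12.6 requires withdrawal on pregnancy. Tests at V3 and V5 would bring the longest on-treatment interval down to 200 days.

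This is an optional improvement, not an error. It contradicts nothing in the plan and does not bear on the trial's conclusions. The benefit is limited to unrecognised pregnancies conceived before V5 in women on active drug: about 0.03 to 0.16 per 100 randomised women. Most early-gestation exposure would still not be prevented.

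That range rests on the 1% per year ceiling, which presumes contraception is used as required and so is not a strict bound; on an assumed unrecognised share of 5% to 25%; on conception spread evenly over dosing; and on equal allocation among these women. The number of women of childbearing potential is not given, so no total for the trial follows.

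It would be too strong to infer that the schedule shows a known foetal risk being ignored, or that early leavers go untested. The documents name no such risk, and sections 11.5 and 12.5 together imply a test at early withdrawal.

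**What to change.** In sections 12.5, 12.6, 11.2.4 and 11.2.6 and in the flow chart, add a pregnancy test for women of childbearing potential at V3 and V5, run on the safety blood already drawn. Keep the test at V6 or early withdrawal.

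The cost is one assay at each of two visits. No new visit or draw is needed, and section 12.5 already gives one 12 ml volume for samplings with and without the pregnancy test. Beyond the protocol wording, the patient information must be updated and approved by the EC/IRB before use. At version 1.4 the change would help mainly German patients with V3 or V5 still ahead, and few in the dose 2 arm because it was being withdrawn. The sponsor could reasonably weigh that narrow reach against the approval work.

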13. OTHER EXPLORATORY ASSESSMENTS

13.1 Plasma level of PXT3003 components

Blood sampling for PK (around 5 mL twice) will be performed before drug administration (trough) and 90 minutes after (peak) at baseline (V1), and at 6-month (V3), 12-month (V5) and 15-month (V6) visits. Pharmacokinetic analysis will require **10 ml of blood to be withdrawn at each point**.

Peak and trough levels of baclofen, naltrexone and 6 β -naltrexol will be measured using a validated LC-MS/MS method developed by Bertin Pharma, France.

Sorbitol will not be dosed for technical reasons: first it is a natural sugar and it is difficult to discriminate between plasma levels of PXT3003-derived sorbitol and sorbitol from other (e.g. dietary) origins, and second after IV injection D-sorbitol plasma levels are measurable for only 10 minutes.

Complete information on blood sampling, conditions of preparation and storage (-80°C) as well as shipment details for PK and Central laboratory contact details will be supplied in a separate technical brochure provided by the central laboratory.

